12.4 Definitions of Evaluable

12.4.1 Evaluable for Toxicity

12.4.1.1 Any subject who received \geq one dose of PD-0325901 and had a \geq Grade 3 PD-0325901-associated toxicity is evaluable for toxicity.

12.4.1.2 In the absence of a \geq Grade 3 toxicity, any subject who completed one full course of therapy is evaluable for toxicity.

12.4.2 Evaluable For Response – Subjects who have completed at least two courses of therapy and have had their first follow-up MRI evaluation. Subjects who did not respond and are later found to have a target tumor other than a plexiform neurofibroma (e.g. malignant peripheral nerve sheath tumor) are not evaluable for response.

12.4.3 Evaluable for Pharmacokinetics – Any subject who has at least 4 samples drawn for pharmacokinetics is evaluable for pharmacokinetics.

12.4.4 Evaluable for Pharmacodynamics – Any subject who has a dermal neurofibroma biopsy for pharmacodynamics prior to starting therapy plus at least one other dermal neurofibroma biopsy is evaluable for pharmacodynamics.

12.4.5 Evaluable for Plasma Cytokines/Growth Factors – Any subject who has at least one sample drawn for plasma cytokines/growth factors prior to starting therapy plus at least one other sample drawn is evaluable for plasma cytokines/growth factors.

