8.3 Toxicities Requiring Removal From Protocol Therapy

Any toxicity defined in section 8.1 or 8.2 that is at least possibly related to study medication that recurs on a reduced dose of PD-0325901. No subject may be dose-reduced more than once.

Any \geq Grade 3 toxicity that is at least possibly due to study drug that does not resolve to \leq Grade 1 within 2 weeks requires removal from protocol therapy.

Development of retinal vein occlusion will also require removal from protocol therapy

Development of glaucoma, intraocular pressure >21 mmHg, or any other significant abnormality on ophthalmic examination (performed by an ophthalmologist) while on study treatment will require removal from protocol therapy. Ophthalmological findings secondary to long-standing Optic Pathway Glioma such as optic nerve pallor or strabismus will NOT be considered significant for the purposes of the study.

The study chair or co-chair should be contacted for any questions regarding toxicity.

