12.3 Statistical Analysis Plan

The basic statistical analysis plan for this proof of concept study will describe the subject population by baseline characteristics: clinical, PK/PD, Quality of Life and pain scores at baseline. Following complete accrual, study logistics will be summarized as per a Consort Diagram with reasons for withdrawal or unable to complete the study tabulated. Appropriate data analysis sets will be defined. The full-analysis set will include data from all subjects who receive ≥ 1 dose of therapy on this study; a safety analysis set will comprise data from subjects in the full-analysis set with any treatment doses. Other data sets (responding, evaluable, and pharmacodynamic/pharmacokinetic data sets) will be defined and will include data from subjects who have the necessary baseline and on-study measurements to provide interpretable results for specific parameters of interest.

Descriptive summaries will be prepared to show sample size, mean, standard deviation, 95% confidence intervals (CIs) on the mean, median, minimum, and maximum for continuous variables and counts, percentages, and 95% CIs on the percentage for categorical variables. For endpoints relating to tumor control, subject well-being, and biomarkers, analyses will be done based on the full-analysis, responding, evaluable, or pharmacodynamic data sets, as appropriate. Time-to-event analyses will be performed with reference to the date of first treatment on this study. Analyses will focus on evaluation of outcomes within each treatment arm and will be largely descriptive in nature as per the sample size justification section. Changes in tumor volumes, etc. will be summarized by medians, ranges, and the corresponding 95% CI. Continuous and categorical variables will also be summarized as appropriate.

Based on the safety analysis set, information regarding study treatment administration, drug dosing and course compliance, safety variables, will be described and summarized. Using data from the pharmacokinetic analysis set plasma concentrations will also be described and summarized. Peak, Trough, Area under the curve and mean serum levels will be compared to

tumor responsiveness. Safety will be assessed via tabulations of AEs and SAEs as well as Diary recordings following treatment dose/course of therapy.

All analyses for outcome results will be based on evaluable subjects, as defined in section 12.4.

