At the end of the trial, we will report poor performance if the treatment is rejected at Stage 1, not meeting the criteria of at least 1 success in 9 cases. If there is no success at Stage II, we will report a failure to reject the null hypothesis using the conditional probability of the added subjects. If the null hypothesis is rejected, the probability of the estimated success rate will be reported and 95% confidence intervals as well as the distribution of changes in tumor size.

An early stopping rule will be invoked to potentially prevent accrual of subjects onto the study in the event that PD-0325901 is associated with a higher than acceptable rate of dose-limiting toxicity (DLT) requiring removal from study (set at 10% or higher) during the first 2 courses. Toxicity will be continuously monitored. As per the 2nd table below, if at any time >2 of the first 10 subjects or 4 or more of the first 15 total subjects are removed for toxicity as per Section 8.3, then accrual will be stopped until the DSMB reviews safety and efficacy data for the study and recommends termination or despite the DLT (because of the benefit:risk assessment or other reasoning) recommends reopening recruitment.

Table 1: Stopping Boundaries requiring DSMB to consider terminating trial

Number of subjects	Trial will be stopped if the number of subjects with severe toxicity is greater than or equal to the number below
10	3 (equivalent to a p-value of 0.07 that the rate of severe toxicity is 10% or less)
15	4 (equivalent to a p-value of 0.055 that the rate of severe toxicity is 10% or less)

Using these rules and the binomial distribution, the chance of putting the trial on hold and potentially stopping early within the first 10 subjects:

True probability of toxicity	Chance of stopping early
.10	7%
.20	32%
.25	47%
.30	62%
.35	74%
.40	83%

In addition, any episode of retinal vein occlusion will halt enrollment until the DSMB reviews the case and the study and recommends termination or despite the DLT recommends reopening recruitment.

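### Sections 12.3 and 12.4.1 give two conflicting populations for toxicity rates, and membership of the 12.4.1 population depends on the toxicity outcome

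*Combined protocol and SAP*

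**What the plan says.** **Section 12.4.1** has two routes into the toxicity-evaluable set. The first needs at least one dose and a Grade 3 or higher "PD-0325901-associated toxicity is evaluable for toxicity", with no minimum exposure. The second applies when there is no Grade 3 or higher toxicity: "any subject who completed one full course of therapy is evaluable for toxicity".

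**Section 12.3** defines a different population: "a safety analysis set will comprise data from subjects in the full-analysis set with any treatment doses". It assigns safety reporting to that population: "Based on the safety analysis set, information regarding study treatment administration, drug dosing and course compliance, safety variables, will be described and summarized". It adds that "Safety will be assessed via tabulations of AEs and SAEs as well as Diary recordings". Its paragraph on analysis sets and outcomes then closes with a general statement: "All analyses for outcome results will be based on evaluable subjects, as defined in section 12.4". Section 12.4 includes the toxicity definition above.

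**Section 8.3** requires removal from therapy for some findings with no grade threshold. Retinal vein occlusion is one. Another is "Development of glaucoma, intraocular pressure >21 mmHg, or any other significant abnormality on ophthalmic examination". Section 10.4 also lets a subject withdraw because of an adverse event that he or she finds intolerable, whatever its grade.

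**The toxicity stopping rule** in 12.3 pauses accrual "if at any time >2 of the first 10 subjects or 4 or more of the first 15 total subjects are removed for toxicity" under Section 8.3.

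**The concern.** A toxicity denominator should be fixed by exposure, not by whether toxicity occurred. Under 12.4.1, two subjects who both stop in course 1 are treated differently according to the grade of their event. The one with a Grade 3 event stays in the set; the one with a Grade 2 event leaves it, even when toxicity was the reason for stopping.

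Toxicity is a secondary aim (1.2.1). The closing sentence of 12.3 can be read as sending toxicity rates to the 12.4 sets, while the safety paragraph just before it uses all dosed subjects. Two analysts could therefore follow the plan and report different toxicity rates from the same data. The choice also distorts in two directions: it makes treatment look better tolerated on removals and worse on Grade 3 or higher events.

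**Working it through.** **1. The plan's own toxicity figures.** The only stated toxicity calculation is the stopping rule. P(X ≥ 3) for a binomial with n = 10:

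| True rate | Computed | Stated |
|---|---|---|
| 0.10 | 0.0702 | 7% |
| 0.20 | 0.3222 | 32% |
| 0.25 | 0.4744 | 47% |
| 0.30 | 0.6172 | 62% |
| 0.35 | 0.7384 | 74% |
| 0.40 | 0.8327 | 83% |

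P(X ≥ 4) with n = 15 and rate 0.10 is 0.0556, against a stated 0.055, which is immaterial. The table reproduces with all of the first 10 subjects as the denominator.

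**2. Who is in which population.**

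| Subject | Safety set (12.3) | Toxicity-evaluable (12.4.1) | Counted by stopping rule |
|---|---|---|---|
| Stops in course 1, drug-associated Grade 3 or higher, removed under 8.3 | Yes | Yes | Yes |
| Stops in course 1, lower-grade finding, removed under 8.3 | Yes | **No** | Yes |
| Stops in course 1, lower-grade event, own choice (10.4) | Yes | **No** | In the denominator only, unless 8.3 applies |
| Completes course 1 | Yes | Yes | Yes |

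The second and third rows are possible. Section 6.1.5 reports six patients with Grade 2 visual events in earlier studies, one of them a retinal vein occlusion. Section 9.3 places the first on-treatment eye examination after course 1 with a window of 2 weeks either side, so it can fall before the course ends.

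**3. Direction.** Let N be the number dosed, g the number removed with a Grade 3 or higher event, and k the number removed in course 1 with only lower-grade toxicity.

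- Removal rate: (g + k)/N in all dosed subjects, g/(N − k) in the 12.4.1 set. The second is smaller whenever k > 0 and g + k < N, because (g + k)(N − k) − gN = k(N − g − k) > 0.
- Grade 3 or higher rate: g/N in all dosed subjects, g/(N − k) in the 12.4.1 set. The second is larger whenever g and k are both above 0.

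**4. Size.** N = 19 is the maximum enrolment in 12.2. The values of g and k are assumptions, since the documents give none. It is also assumed that every Grade 3 or higher subject is removed, that no other removals for toxicity occur, and that everyone else completes course 1.

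| g | k | Removals, all dosed | Removals, 12.4.1 set | Grade 3+, all dosed | Grade 3+, 12.4.1 set |
|---|---|---|---|---|---|
| 2 | 1 | 3/19 = 15.8% | 2/18 = 11.1% | 2/19 = 10.5% | 2/18 = 11.1% |
| 2 | 2 | 4/19 = 21.1% | 2/17 = 11.8% | 10.5% | 2/17 = 11.8% |
| 2 | 3 | 5/19 = 26.3% | 2/16 = 12.5% | 10.5% | 2/16 = 12.5% |
| 4 | 1 | 5/19 = 26.3% | 4/18 = 22.2% | 4/19 = 21.1% | 4/18 = 22.2% |
| 4 | 3 | 7/19 = 36.8% | 4/16 = 25.0% | 21.1% | 4/16 = 25.0% |

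Exact 95% intervals are wide at this size. For g = 2 and k = 3 they are 9.1% to 51.2% for removals in all dosed subjects and 1.6% to 38.3% in the 12.4.1 set. The difference between the sets is nevertheless systematic.

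**The case against.** The strongest reply is that 12.3 already settles the matter. It gives safety its own paragraph and its own all-dosed population, and links the evaluable sets to tumour control, well-being and biomarkers. The closing sentence is general and does not name safety, so the specific assignment could be read as governing. Section 10.4 requires every adverse event to be recorded, and 12.3 tabulates reasons for withdrawal. On that reading, early lower-grade removals appear in the safety tables and the disposition summary.

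Much of this stands. A reader might infer that such subjects vanish from the toxicity results altogether; the documents do not support that. They are lost only from rates computed on the 12.4.1 set. But the reply leaves 12.4.1 with no stated use, and the closing sentence covers all of 12.4 without excepting toxicity.

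A reader might also infer that the stopping rule loses sensitivity. If the rule were applied to 12.4.1-evaluable subjects, with a true removal rate of 30% and a quarter or a half of removals being lower-grade in course 1 (assumptions), the chance of a hold within 10 subjects would be 45.4% or 25.3% instead of 61.7%. That is not the plan's rule. Its text counts Section 8.3 removals among the first 10 or 15 subjects, and neither the text nor the boundary table restricts this to evaluable subjects.

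Finally, the eye-finding route is narrow. The first scheduled examination falls around the end of course 1, and Section 2.2 reports retinal vein occlusions in the phase 1 trial only after 13, 15 and 36 weeks. This bears on how many subjects would be affected. It does not remove the conflict, and withdrawal under 10.4 can occur at any time.

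**Conclusion.** The point holds as a conflict of populations. Section 12.3 summarises safety in all dosed subjects but bases outcome results on the 12.4 sets, and 12.4.1 selects on the toxicity outcome. If 12.4.1 is used for toxicity rates, removals for toxicity are understated and the Grade 3 or higher rate is overstated.

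The size depends on how many subjects stop in course 1 with only lower-grade toxicity, which the documents do not let one predict. With 1 to 3 such subjects among 19 and 2 Grade 3 or higher removals, the removal rate falls by 4.7 to 13.8 percentage points and the Grade 3 or higher rate rises by 0.6 to 2.0 points. If there are none, these two rates are not biased in this way.

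The stopping rule, its boundaries and its stated operating characteristics are not affected as written. The issue concerns reported toxicity rates only and should be corrected because the ambiguity is easily removed.

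**What to change.** Replace both 12.4.1.1 and 12.4.1.2 with one definition: every subject who received at least one dose is evaluable for toxicity. Deleting 12.4.1.2 alone would not do, because the Grade 3 condition in 12.4.1.1 would remain.

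In 12.3, state that all AE, SAE and toxicity rates use this set, which is the safety analysis set already defined there, and limit the closing sentence on outcome results to the non-safety outcomes.

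The cost is a wording amendment to two sections. It needs no added subjects or data collection, since 10.4 already has every adverse event recorded. No dose, removal criterion or stopping boundary changes.

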12.2 Statistics and Feasibility

The primary objective of this study is to determine if there is an adequate level of disease responsiveness to PD-0325901 in adolescents and adults with NF1 and inoperable plexiform neurofibromas.

Sample Size

Minimum: 9 evaluable subjects Maximum: 19 evaluable subjects Target: 17 evaluable subjects. To allow for 10% unevaluable subjects, a maximum of 19 subjects will be enrolled. We anticipate enrollment to be completed in 24 months with primary outcome measure defined in 30 months.

The sample size for this trial is based on three primary factors: safety based on risk versus benefit; efficacy of 25% response rate and power of 80% to achieve feasibility if this rate were true. In order to balance these factors, we propose a two stage Simon Optimal Design³². Two stage designs are designed to provide an overall Type I error that is based on the probability of stopping at the end of Stage 1 plus the conditional probability of rejecting the drug given one passed Stage 1 to get to Stage 2. Thus, the overall Type I error was set at 5% and power at 80%. We assume a null hypothesis success rate of 5% versus a treatment with a 25% response rate.

Stage 1 will consist of 9 subjects to provide evidence of effectiveness and safety. If at least 1 of the 9 subjects achieves a radiographic response ($\geq 20\%$ reduction in tumor volume) the study will be allowed to recruit the total sample size of 17 evaluable subjects. The Stage I boundary is the same 0 of 9. The second stage of the design requires only 3 or more of the 17 subjects to have a positive response. If the null hypothesis is true, there is a 63% chance of terminating after Stage 1. If the probability of success is actually 0.25, there is a 92% chance that 1 or more subjects will exhibit a 20% reduction in tumor volume at Stage 1. Thus, it is expected that the trial will continue with continuous recruitment if the 25% success rate is correct.

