For safety reasons, subjects who do not achieve at least a 15% reduction in tumor volume will not be continued beyond 8 cycles, as the likelihood of achieving a response (20% reduction in tumor volume) by 12 months is minimal. These subjects will be discontinued from the trial and counted in an "Intent to Treat" analysis as evaluable and as failures. If there are no subjects with a response (20% or more reduction in tumor volume) by the end of 8 cycles, but one or more with a 15% or more tumor volume reduction, recruitment will be suspended until the decision on futility (0 of 9 with at least 20% or more reduction in tumor volume after 12 cycles) or successful continuation can be definitively recommended. That is, if there are a number of subjects with 15% up to but not achieving a 20% reduction in tumor volume, the study will follow those subjects up to their post cycle 12 visit to determine if the recruitment can be restarted. If none of these 9 achieves a 20% tumor volume reduction by 1 year, the study will be terminated.

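### Section 12.4.2 excludes wrong-tumor subjects only if they did not respond, early leavers are treated inconsistently, and the success rule is stated for exactly 17 evaluable subjects

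*Combined protocol and SAP*

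**What the plan says.** Section 12.4.2 defines evaluable for response as "Subjects who have completed at least two courses of therapy and have had their first follow-up MRI evaluation". It then declares not evaluable "Subjects who did not respond and are later found to have a target tumor other than a plexiform neurofibroma", with malignant peripheral nerve sheath tumor as its example.

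Three other places bear on who is counted.

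- The last sentence of Section 12.3 reads: "All analyses for outcome results will be based on evaluable subjects, as defined in section 12.4".
- Earlier in 12.3, a full-analysis set of everyone with at least one dose is defined. Tumor-control endpoints may use that set, the responding set or the evaluable set, whichever is judged suitable.
- Section 12.2 takes subjects stopped at 8 cycles for less than a 15% volume reduction and counts them in an intent-to-treat "analysis as evaluable and as failures".

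On numbers, Section 12.2 states: "To allow for 10% unevaluable subjects, a maximum of 19 subjects will be enrolled". The final rule is: "The second stage of the design requires only 3 or more of the 17 subjects to have a positive response". The same section lists a target of 17 evaluable subjects and a maximum of 19 evaluable subjects.

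**The concern.** A denominator should be fixed without looking at the outcome. Under 12.4.2, two subjects with the same late tumor finding are handled differently: the non-responder is removed, the responder is kept in numerator and denominator. Section 4.1.2 does not require histology when clinical and imaging findings agree, so such a finding can surface after treatment starts.

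The second issue is early departure. A subject who stops before finishing two courses, or who has no follow-up MRI, is not evaluable and so does not count as a failure. Toxicity is one route: the stopping rule in 12.3 concerns toxicity "requiring removal from study (set at 10% or higher) during the first 2 courses", and anyone removed before finishing course 2 falls outside the response set. The end-of-treatment MRI in Section 9.7 can make a subject who leaves after course 2 or 3 evaluable, but not one who leaves sooner. If early leavers are mostly non-responders, the reported rate overstates the rate among treated subjects.

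The third issue is the decision rule. If the number evaluable is not 17, the plan does not say what counts as success, and the choice could be made after the responses are known.

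**Working it through.** **Inputs.** From 12.2: null rate 5%, alternative 25%, type I error 5%, power 80%; continue if at least 1 of 9 respond; success if at least 3 of 17; 10% unevaluable; 19 enrolled. The documents give no frequency for wrong-tumor findings and no response rate for early leavers; both are assumptions below.

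**1. The plan's own design.** P(success) is the sum over x ≥ 1 of Bin(x; 9, p) × P(Y ≥ 3 − x), with Y ~ Bin(8, p).

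- p = 0.05: x = 1 gives 0.29854 × 0.05724 = 0.01709; x = 2 gives 0.06285 × 0.33658 = 0.02115; x ≥ 3 gives 0.00836. Total **0.0466**.
- p = 0.25: 0.22525 × 0.63292 = 0.14257; 0.30034 × 0.89989 = 0.27027; 0.39932. Total **0.812**.
- Stopping after stage 1 under the null: 0.95^9 = 0.630. Enrolment: 17/0.9 = 18.9, so 19.

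The stated 5%, 80%, 63% and 19 all reproduce. The design is sound for exactly 17 evaluable subjects whose evaluability is unrelated to response.

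**2. Tumor-type rule.** Assume one of the 17 places is affected, that subject responds with probability 0.05, and a non-responder is replaced by another subject at 0.05. The place then yields a response with probability 0.05 + 0.95 × 0.05 = 0.0975; the other 16 stay at 0.05. Type I error becomes **0.0537** if the place is in stage 1 and **0.0523** if in stage 2. With a symmetric exclusion and replacement it stays at 0.0466.

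**3. Early leavers.** If a fraction q of treated subjects is dropped and none of them responds, the reported rate is the all-treated rate divided by (1 − q). At 25% and q = 0.10: 0.25/0.90 = **27.8%**. For the smallest successful result, 3/17 = 17.6% (exact 95% CI 3.8% to 43.4%) against 3/19 = 15.8% (3.4% to 39.6%) if two early leavers are counted as failures.

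**4. Chance of missing 17.** With 19 enrolled and each independently unevaluable with probability 0.10, fewer than 17 evaluable means at least 3 unevaluable: 1 − (0.1351 + 0.2852 + 0.2852) = **0.29**. This applies when enrolment runs to 19.

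**5. Keeping at least 1 of 9 and at least 3 in total, for other numbers evaluable.** Same formula, with Y ~ Bin(n − 9, p):

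| Evaluable n | Type I error | Power at 25% |
|---|---|---|
| 14 | 2.9% | 71.1% |
| 15 | 3.5% | 75.1% |
| 16 | 4.1% | 78.5% |
| 17 | 4.7% | 81.2% |
| 18 | 5.3% | 83.5% |
| 19 | 5.9% | 85.3% |

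These take 5% and 25% as rates among evaluable subjects. Below 17 the type I error is safe and power falls under 80%; above 17 the type I error passes 5%.

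**The case against.** Several points on the other side stand. Evaluable-for-response denominators are an ordinary choice, and 12.2 sizes the trial in evaluable subjects, so 5% and 25% most naturally refer to that set. On that reading, with departure unrelated to response, dropping early leavers does not inflate type I error; with fewer than 17 the table shows it falls. A reader might infer that 12.4.2 breaks the 5% level through early leavers. That needs an all-treated null, which the plan does not state, together with poorer response among those who leave.

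A reader might also infer that the trial fails automatically with fewer than 17 evaluable, with a large loss of power. No section says so. The natural reading keeps the count of 3, which makes this a gap in wording with a moderate power cost.

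Nor should the toxicity limits be read as planning for a 20% early loss. The hold rule does let 2 "of the first 10 subjects or 4 or more of the first 15 total subjects are removed for toxicity as per Section 8.3" or 3 of 15 pass. But 12.3 treats 10% or higher as unacceptable, and not every Section 8.3 removal comes before two courses are complete.

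On tumor type, 4.1.2 asks that histology be considered when malignant change is suspected, and 4.1.3 requires central MRI review before entry, so such findings may be rare. Section 13 defines response only for a plexiform neurofibroma, so it is arguable whether a wrong-tumor subject can respond at all. That argues for excluding both kinds of subject, which 12.4.2 does not do. Detection without routine histology may still depend on outcome, so a symmetric rule reduces the bias but may not remove it.

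Finally, 12.3 does mention the full-analysis set for tumor endpoints. The accurate description is that its text conflicts with its closing sentence, not that the plan ignores treated subjects.

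**Conclusion.** The point holds at a moderate level; the wording should be corrected before the data are analysed.

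- The tumor-type exclusion is outcome-dependent as written and can only push the rate up. Its frequency is unknown. Type I error of about 5.2% to 5.4% rests on one affected subject, a 5% response probability and replacement when a non-responder.
- Sections 12.2, 12.3 and 12.4.2 disagree on whether early leavers enter the response rate. Reporting 27.8% for a true 25% rests on 10% loss and on every excluded subject being a non-responder.
- The decision rule is undefined away from 17. At the plan's own 10% rate, with 19 enrolled, falling below 17 has a 29% chance; 18 or 19 is also permitted by 12.2.

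The design calculation itself is correct. The documents do not support a claim of gross loss of error control or power, nor a claim that the primary analysis must move to all treated subjects.

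**What to change.** 1. In 12.4.2, delete the condition on non-response, so that a target tumor found not to be a plexiform neurofibroma is excluded whatever its response. Apply the same rule in every efficacy set.
2. Reconcile 12.2, 12.3 and 12.4.2. The evaluable set may remain primary. Beside it, report the response rate among all subjects with at least one dose, after the same tumor-type exclusion, counting anyone without a documented response as a non-responder.
3. In 12.2, state that the test uses the first 17 evaluable subjects, with any further ones reported descriptively. State also that 3 or more responses remains the rule below 17, and give the type I error and power for 16, 15 and 14 from the table above.

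The cost is wording only: no added subjects, visits or data. The all-treated rate will look slightly less favourable, and the plan must acknowledge that 80% power does not hold below 17 evaluable. Making the all-treated set primary is optional. If 25% is really the evaluable rate and early leavers count as failures, the all-treated rate at 10% lost is 0.25 × 0.9 = 22.5% and power on 17 treated subjects is 74.5%; at an assumed 20% lost the rate is 20% and power 66.3%.
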